#### 4.2. Description of the trial design.

Open Multicentre Randomized Controlled Trial, in parallel groups, based on treatment with progesterone comparing the placement of a prophylactic cervical pessary with usual management in singleton pregnancies at high-risk of PTB due to a history of at least one previous preterm delivery and/or a history of late abortion.

#### 4.3. Flowchart.

#### 4.4. Description of the medical device and the treatment regimen.

The cervical pessary is a vaginal device (silicone ring) that is used to treat pregnant women for preventing spontaneous preterm birth. This device can be easily placed around the uterine cervix without pain (see annex I).

Women with a singleton pregnancy at 12+0 – 18+0 weeks of gestation and a history of at least one previous preterm delivery before 34+0 weeks and/or a history of late abortion attending the reference hospital for a preventive examination will be informed of the ongoing trial. The patient will be advised of the intended therapeutic effect and possible side effects. If they agree and after obtaining their informed consent, they will be randomised according to either progesterone (=control group) or cervical pessary placement up to 37+0 weeks (= pessary group).

If the pregnant woman is assigned to the pessary group and after having excluded a vaginal infection the pessary will be inserted directly. This procedure does not need anaesthesia and it does not need to be done in a surgery room. After the insertion of the pessary the correct fit of the pessary is verified by transvaginal ultrasound and in case it does not fit perfectly, it can easily be adjusted.

In the control-group, the pregnant women be treated with progesterone. Utrogestan is one of the normal drugs in China to prevent spontaneous preterm birth, the Utrogestan used in this study is from Laboratories Besins International. For the enrollment, pregnant women in the control group were treated by 200 mg QN, it is used for 34 gestational weeks.

The pessary will be removed at 37+0 weeks of gestation, or before if any unexpected event occurs (see 4.6). After insertion of the pessary the obstetrical management during the remainder of the pregnancy will be usual management.

Further surveillance of the pregnancy will not be influenced by the participation on the study.

#### **4.6. Completion and interruption criteria of the study or the subjects.**

The pessary will be removed at 37+0 weeks of pregnancy. The indications to remove them before this time will be: active bleeding stronger than period bleeding, persistent contractions after tocolysis and premature rupture of the membranes after 34+0 weeks.

After removing the pessary, the obstetrical management will be done as usual and will not be influenced by the study.

#### 4.10. Selection and withdrawal of subjects

##### **4.10. 1 Inclusion criteria.**

- Women with a singleton pregnancy and a history of at least one previous preterm delivery before 34+0 weeks and/or a history of late abortion
- 12+0 -18+0 weeks of gestation
- Minimal age of 18 years
- Informed consent signature

##### **4.10. 2 Exclusion criteria.**

- The previous preterm delivery is iatrogenic proterm labor
- Major fetal abnormalities (requiring surgery or leading to infant death or severe handicap)
- The pregnant woman with severe cervical erosion, cervical polyp, hemorrhage and the doctors think she could not use cerclage pessary

- The pregnant woman with uterine cervicitis
- The pregnant woman that has been confirmed premature birth
- Cerclage prior to randomisation
- Uterine malformation
- Placenta previa totalis
- Active vaginal bleeding at the moment of randomization
- Spontaneous rupture of membranes at the time of randomization
- Silicone allergy
- Painful regular uterine contractions
- The pregnant woman have the indication of operation cervical cerclage
- Current participation in an other RCT

#### **4.10. 3. Withdrawal criteria.**

If a participant may voluntarily withdraw from treatment or if it is necessary to remove the pessary due to the conditions described before, the patients will be followed as usual until delivery (intention-to-treat analysis).

Replacement of patients is not applicable in this trial.

#### **4. 10. 4. Rescue treatment criteria.**

According the current guide and expert advice, when the routine follow-up examination, the rescue cervical cerclage may be adopted when the secondary cervical shortening occurs.

#### **4.11. Treatment of Subjects**

##### **4.11.1. Treatments to be administered.**

The pessary will be inserted during a preventive examination in pregnancy in the examination room. This procedure does not need anaesthesia and it does not need to be done in a surgery room. After the insertion of the pessary the correct fit of the pessary is verified by transvaginal ultrasound and in case it does not fit perfectly, it can easily be adjusted. pregnant women in the control group were treated by 200 mg QN, it is used for 34 gestational weeks. The pessary or cerclage will be removed at 37+0 weeks of gestation, or before if any unexpected event occurs (see 4.6).

After insertion of the pessary the obstetrical management during the pregnancy will be usual management.

Further surveillance of the pregnancy will not be influenced by the participation on the study.

## **5. Assessment of Safety**

### **5.1. Procedures to record and report adverse events.**

If a serious and unexpected adverse effect occurs during treatment, it will be notified to the study Sponsor. The Department of Obstetrics and Gynecology of the Sponsor will fill the side effects document to notify it to the Ethics Committee.

The patient affected by the adverse effect will be followed more intensively during the first days and if nothing else occurs, she will return to the standard control.

### **5.2. Definitions.**

Adverse Event (AE): Any untoward medical occurrence in a patient or clinical investigation participants administered a medicinal product, which does not necessarily have to have a causal relationship with this treatment (the study medication). An AE can therefore be any unfavourable and unintended sign (including an abnormal laboratory finding), symptom or disease temporally associated with the use of the study medication/procedure, whether or not considered related to the study medication.

Adverse Reaction (AR): All untoward and unintended responses to a medicinal product related to any dose. The phrase "responses to a medicinal product" means that a causal relationship between a study medication and an AE is at least a reasonable possibility, i.e., the relationship cannot be ruled out.

All cases judged by either the reporting medically qualified professional or the sponsor as having a reasonable suspected causal relationship to the study medication / procedure qualify as adverse reactions.

Serious Adverse Event (SAE): A serious adverse event is any untoward medical occurrence that at any dose: Results in death; is life-threatening, NOTE: The term "life-threatening" in the definition of "serious" refers to an event in which the participant was at risk of death at the time of the event; it does not refer to an event which hypothetically might have caused death if it were more severe; Requires inpatient hospitalization or prolongation of existing hospitalization; Results in persistent or significant disability/incapacity, or is a congenital anomaly/birth defect.

Other important medical events: Other events that may not result in death, are not life threatening, or do not require hospitalization, may be considered a serious adverse event when, based upon appropriate medical judgment, the event may jeopardize the patient and may require medical or surgical intervention to prevent one of the outcomes listed above.

To ensure no confusion or misunderstanding of the difference between the terms "serious" and "severe", which are not synonymous, the following note of clarification is provided:

The term "severe" is often used to describe the intensity (severity) of a specific event (as in mild, moderate, or severe myocardial infarction); the event itself, however, may be of relatively minor medical significance (such as severe headache). This is not the

same as "serious," which is based on patient/event outcome or action criteria usually associated with events that pose a threat to a participant's life or functioning as defined in the bullet points above. Seriousness (not severity) serves as a guide for defining regulatory reporting obligations.

Serious Adverse Reaction (SAR): An adverse event (expected or unexpected) that is both serious and, in the opinion of the reporting investigator, believed with reasonable probability to be due to one of the study treatments, based on the information provided.

Suspected Unexpected Serious Adverse Reaction: A serious adverse reaction, the nature or severity of which is not consistent with the applicable product information (e.g. Investigator's Brochure for an unapproved investigational product or summary of product characteristics for an approved product).

### **5.3. Procedures for immediate notification of serious or unexpected adverse events.**

All AEs occurring during the study /or observed by the investigator or reported by the participant, whether or not attributed to study medication, will be recorded on the CRF.

The following information will be recorded: description, date of onset and end date, severity, and assessment of relatedness to study medication, other suspect drug or device and action taken. Follow-up information should be provided as necessary.

AEs considered related to the sanitary device, as judged by a medically qualified investigator, will be followed until resolution or the event is considered stable. All related AEs that result in a participant's withdrawal from the study or are present at the end of the study, should be followed up until a satisfactory resolution occurs.

It will be left to the investigator's clinical judgment whether or not an AE is of sufficient severity to require the participant's removal from treatment. A participant may also voluntarily withdraw from treatment due to what he or she perceives as an intolerable AE. If either of these occurs, the participant must undergo an end of study assessment and be given appropriate care under medical supervision until symptoms cease or the condition becomes stable.

A medically qualified investigator will assess the relationship of AEs to the study medication.

All SAEs must be reported to the main investigator. He will perform an initial check of the report, request any additional information, and he will notify it to the Ethics Committee and CFDA. All SAE information will be recorded. It may be appropriate that some SAEs do not require immediate reporting but this must be justified. Justification might be determined, for example, by admission to hospital, or prolongation of hospitalization, where this is to be expected in the underlying disease or condition.

All adverse events (AE) life-threatening or resulting in death will be notified within 24 hours. All AE that are not life-threatening will be notified within 15 days. The rest of AE will be recorded and analyzed at the end of the study.

## **6. Efficacy assessment**

### **6.1. Specification of efficacy parameters: Primary and secondary endpoints.**

This study aims to investigate the benefit of a prophylactic cervical pessary treatment in women at high risk of PTB due to a history of at least one previous preterm delivery and/or a history of late abortion on the perinatal outcome .

### **6.2. Methods and timing to assess records and analyze the efficacy parameters.**

The pregnant women will be assessed according to usual obstetrical management in a high-risk pregnancy.

	Regular Preventive Exam 12+0-18+0 WoG	Regular Preventive Exam 34+0 WoG	Postnatal evaluation
Study procedure	study inclusion		
Informed consent signature	x		
randomisation	x		
Pessary placement	x (Pessary-Group)		
Pessary/cerclage removal		x	
progesterone	x	x	
physical exams			
Abdominal US	x	x	
Vaginal US			
BV/trichomonad/mycete			
Neonatal examination			x
Ages & Stages test (corrected age)			

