## **2.2. Description of the study population.**

Women with a singleton pregnancy at 12 – 18 weeks of gestation and a history of at least one previous preterm delivery before 34+0 weeks and/or a history of late abortion attending the reference hospital and who do not fulfil the exclusion criteria the study will be proposed. The patients will be informed of the intended therapeutic effect and possible side effects. If they agree and after obtaining their informed consent, they will be randomised according to either usual management with rescue cerclage placement only when (and as soon as possible) a cervical shortening below 25 mm occurs (=control group) or cervical pessary placement (= pessary group). Pessaries or cerclage shall be placed up to 37+0 weeks of gestation. Serial cervical length measurements shall be conducted every 4 weeks in order to diagnose cervical shortening as soon as possible in the control group.

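### The visit table in section 6.2 removes the pessary or cerclage at 34+0 weeks, three weeks before the 37+0 set in the protocol text; the table should be corrected.

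*Protocol*

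**What the plan says.** Four places in the protocol text give the planned end of device treatment, and all give the same age:

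- Section 2.2, pessary and cerclage: "Pessaries or cerclage shall be placed up to 37+0 weeks of gestation".
- Section 4.4, pessary only: "The pessary will be removed at 37+0 weeks of gestation, or before if any unexpected event occurs".
- Section 4.6, pessary only: "The pessary will be removed at 37+0 weeks of pregnancy".
- Section 4.11.1, pessary and cerclage: "The pessary or cerclage will be removed at 37+0 weeks of gestation".

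Section 4.6 then lists the grounds for taking the pessary out sooner: bleeding heavier than a period, contractions that persist despite tocolysis, and "premature rupture of the membranes after 34+0 weeks". Section 4.10.3 also allows for voluntary withdrawal from treatment. None of these is a routine removal at 34+0.

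The table in section 6.2 has three columns: entry at 12+0 to 18+0, 34+0, and postnatal. The row "Pessary/cerclage removal" carries one mark, under "Regular Preventive Exam 34+0 WoG". There is no column for 37+0.

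**The concern.** The age at removal fixes how long the tested intervention lasts, so it should have one value throughout the protocol. Site staff often work from the visit table. One who did so here would take the device out at 34+0; one who followed the text would leave it to 37+0.

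The outcomes at stake are those that depend on births from 34+0 to 36+6. That interval is what separates the before-34 from the before-37 secondary outcome in section 4.1.2, and the log-rank comparison of time to birth in section 7.1 runs across it. If some women lose the device at 34+0, they pass through that interval untreated, and any effect the pessary has there is diluted in the pessary group as randomised. The removal row also covers cerclage, which is the rescue treatment under sections 2.2 and 4.10.4, so control women given a cerclage could be affected as well.

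**Working it through.** **1. The plan's own figure.** Section 7.2 gives 121 per group for 0.924 against 0.800, two-sided 5% test, pooled variance, 80% power. With mean proportion 0.862:

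n = [1.960 × √(2 × 0.862 × 0.138) + 0.842 × √(0.924 × 0.076 + 0.800 × 0.200)]² / 0.124² = (0.956 + 0.404)² / 0.015376 ≈ 120.3, rounded up to 121.

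The figure reproduces (power at 121 is 80.2%). It contains no term for treatment duration, so this point does not change it.

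**2. Text against table.**

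| Place | Device named | Planned removal |
|---|---|---|
| 2.2 | pessary, cerclage | 37+0 |
| 4.4 | pessary | 37+0 |
| 4.6 | pessary | 37+0 |
| 4.11.1 | pessary, cerclage | 37+0 |
| 6.2 table | pessary, cerclage | 34+0 |

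The table cannot be read as a permitted exception, because reaching 34+0 is not a listed ground for early removal. The membrane-rupture criterion in 4.6 applies only after 34+0 and so presupposes a pessary still in place then. Routine removal at 34+0 would leave it almost nothing to act on.

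Sections 4.4 and 4.11.1 use progesterone to 34 weeks (as their wording is most naturally read), and the progesterone row is marked at 34+0. That visit fits the drug but not the device. A plausible explanation is that the drug's stop visit was also used for the device.

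**3. Treatment time lost.** Entry is at 12+0 to 18+0.

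- Wear to 37+0: 37 − 12 = 25 weeks, down to 37 − 18 = 19 weeks.
- Wear to 34+0: 34 − 12 = 22 weeks, down to 34 − 18 = 16 weeks.
- Loss: 3 weeks, which is 3/25 = 12% to 3/19 = 15.8%.

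**4. What the dilution could look like.** The protocol gives none of the inputs needed, so these are assumptions: control rate of birth before 37 weeks c = 40%; relative risk r = 0.60 with removal at 37+0; late share L = 50% of these births falling at 34+0 to 36+6; no effect after removal. If a share s of pessary women have removal at 34+0, the pessary-group rate is

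p = c(1 − L)r + cL[s + (1 − s)r].

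| s | p | p/c | Power, 121 per group |
|---|---|---|---|
| 0 | 0.12 + 0.20 × 0.60 = 0.24 | 0.60 | 76% |
| 0.5 | 0.12 + 0.20 × 0.80 = 0.28 | 0.70 | 50% |
| 1 | 0.12 + 0.20 × 1.00 = 0.32 | 0.80 | 25% |

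Over c = 30% to 50%, r = 0.6 to 0.7 and L = 50% to 70%, removal at 34+0 in every pessary woman gives a relative risk of 0.80 to 0.91. The calculation leaves out any early cerclage removal among controls. It shows what could happen if sites followed the table; it does not forecast that they will.

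**The case against.** The strongest reply is that the protocol is not really ambiguous. Four sections agree on 37+0, including both treatment sections and the completion criteria, and a site that routinely removed the device at 34+0 would breach them. This stands: it settles 37+0 as the intended age and makes the table mark the error.

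A second reply is that the table is weak evidence of a visit schedule. Section 6.2 defers to usual obstetric care, and several rows (physical exams, vaginal ultrasound, infection tests, Ages & Stages) have no marks, although sections 4.4 and 4.11.1 require a transvaginal ultrasound check after insertion and 4.4 requires vaginal infection to be excluded first. The four-weekly cervical measurements in 2.2 have no columns either. This stands in part. The marks that remain sit where they should (placement at entry, neonatal examination after birth), so the 34+0 mark looks genuine, but a lost column cannot be wholly excluded.

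A reader might also infer more than the protocol supports:

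- *That sites have no visit at which to remove the device at 37+0.* A missing column is not a missing visit. Surveillance follows usual care, and an ordinary 37-week visit would serve.
- *That removal timing would confound the comparison.* Each centre has its own randomisation list (section 10) and all randomised women are analysed (section 7.4). Differing site practice would vary or dilute the treatment delivered; it would not by itself unbalance the arms. Because the trial is open, timing chosen woman by woman is conceivable, but nothing in the protocol provides for it.
- *That the result could not be tied to one defined treatment.* The text defines one treatment, to 37+0. The table creates a risk of departures from it.

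**Conclusion.** The contradiction is real and lies in current text: the section 6.2 table places device removal three weeks earlier than sections 2.2, 4.4, 4.6 and 4.11.1. Followed literally, the table would cut planned wear by 12% to 16%.

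The consequence is conditional and limited. It arises only where sites follow the table, only if the pessary still has an effect after 34+0, and only for secondary outcomes that extend past 34+0. Births before 34+0 are untouched, as is the sample-size calculation, and no effect on the stated primary outcome (the child's birth and survival) is shown. The relative risks and power losses above rest on assumed rates and cannot be taken as estimates for this trial.

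This is a low-cost correction of an internal inconsistency. It is worth making but falls short of a must-fix.

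**What to change.** In the section 6.2 table, add a 37+0 column and move the device-removal mark into it. Leave the progesterone stop, and the abdominal ultrasound already marked there, at 34+0. Sections 2.2, 4.4, 4.6 and 4.11.1 need no change on this point.

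Record the actual date of and reason for removal on the CRF if it does not already hold them; the CRF is not part of the protocol text, so this cannot be checked here. Any removal at 34+0 made under the present table could then be identified and reported.

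The cost is one table edit and at most two data items. No patients are added, and no procedures either, since the text already requires removal at 37+0.

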## **7. Statistics**

### **7.1. Description of statistical methods.**

A descriptive analysis by preterm birth will be carried out calculating means and medians for quantitative variables and proportions for categorical variables.

Two-sided Z-tests will be used for comparing among exposure and outcomes groups per pregnancy. A multivariate logistic regression will be fitted to control for possible confounders. Relative risks and 95% confidence interval will be calculated for the outcomes.

All analysis will be carried out with SPSS® 19.0 statistical package (IBM Company SPSS Inc. Headquarters, Chicago, Illinois. USA). Statistical significance will be accepted in all cases with a  $p < 0.05$ .

Outcome	Statistical Test
Birth before 34 Weeks of Gestation	Two-sided Z-Test (RR, 95% CI)
Time to Birth	Log-rank test (HR, 95% CI)
Birthweight	Multilevel model (mean $\pm$ SD)
Fetal / Neonatal Death	Two-sided Z-Test (RR, 95% CI)
Neonatal Morbidity	Two-sided Z-Test (RR, 95% CI)
Need for Hospitalization	Two-sided Z-Test (RR, 95% CI)
Days of Hospitalization	Two-sided Z-Test (RR, 95% CI)
Maternal Adverse Events	Two-sided Z-Test (RR, 95% CI)
Pessary Intolerance	Two-sided Z-Test (RR, 95% CI)
Vaginal Infections	Two-sided Z-Test (RR, 95% CI)

the complete data set for the secondary endpoints will be available after the last women enrolled in this study has given birth, so the analysis of these outcome parameter will be done right after this event.

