## **2. Rationale**

### **2.1. Justification of the relevance of the trial.**

Preterm birth complicates 13% of all pregnancies worldwide and is the most important cause of neonatal morbidity and mortality. Although disability-free survival rates have increased over the years as a result of improved facilities and treatments, preterm birth is still accountable for 75% of all perinatal deaths and >50% of morbidities. Women with a history of a preterm delivery have a distinctly increased risk to deliver preterm in a subsequent pregnancy. This risk ranges from 11,1% with one previous preterm delivery up to 28% for two previous preterm deliveries. This also applies to women with a history of a second trimester fetal-loss after 20 weeks of gestation who show an increased risk of 12% for preterm birth in a subsequent pregnancy. Yet another independent risk factor for PTB is a previous cervical surgery; after a single surgical conisation the risk of PTB increases almost 5 fold and after two even 10-fold. One treatment option for prevention of preterm birth is a cervical pessary. A cervical pessary is a silicone ring with a smaller diameter to be fitted around the cervix and a larger diameter to fix the device against the pelvic floor. This effectively rotates the cervix toward the posterior vaginal wall and corrects the cervical angle. A prospective-randomised trial by Goya et. al proved a significant reduction of the preterm delivery rate in singleton pregnancies with cervical shortening ( $\leq 25$  mm, 18-22 weeks of gestation) after placement of a pessary compared to expectant management. In a cohort analysis by Alfirevic et al. of asymptomatic women with a singleton pregnancy and a history of preterm birth and a short sonographic cervix the placement of a cervical pessary proved to be as effective as cerclage or treatment with 200 mg vaginal progesterone in reducing the preterm birth rate. A pilot study investigating the effect of pessary treatment in asymptomatic women with a singleton pregnancy and a history of at least one cold knife conisation and a short sonographic cervix suggest a beneficial effect on the prolongation of the pregnancy. In the one Cochrane review available concerning pessary therapy the authors detail a significant decrease in the incidence of spontaneous preterm birth in women with a short cervix when compared with expectant management: PTB less than 37 weeks'

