## **7.2. Expected number of subjects to be included.**

Group sample size of 121 in Group 1 and 121 in Group 2 achieve 80% power to detect a difference between the group proportions of 0,1240. The proportion in Group 1 (the treatment group) is assumed to be 0,8 under the null hypothesis and 0,9240 under the alternative hypothesis. The proportion in Group 2 (the control group) is 0,8000. The test statistic used is the two-sided Z test with pooled variance. The significance level alpha of the test was 5 %. To account for a drop out rate around 20%, sample size of 121 in each group, overall  $n=242$  women will be recruited.

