## **10. Data Management and Registry File**

Patient's participation in the study will be annotated into the medical history. The main investigator will perform a list with the participant's names, ID numbers and codes. He also will have a file with all the information referring to the study. All the data will be collected in a database that will be accessed worldwide. The randomisation will be done on a computer basis. Once entering in the website, if the patient fulfils the inclusion criteria, the computer generated list will randomise the patient to "pessary" or "control" group. The excluded patients will be also collected in the database. Every participating centre will have its own randomisation list, and it will be accessible with a username and password. The trial staff will ensure that the participants' anonymity is maintained. Only a participant ID number on the CRF and in the electronic database will identify the participants. All documents will be stored securely and only accessible by trial staff and authorized personnel. The study will comply with the Data Protection Legislation that requires data to be anonymized as soon as it is mandatory to do so.

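### The powered comparison is an unadjusted pooled Z test despite a 2.5-fold risk gradient by obstetric history in section 2.1; a small, nearly free gain in precision is given up

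*Protocol*

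**What the plan says.** Protocol section 7.1 sets the between-arm method: "Two-sided Z-tests will be used for comparing among exposure and outcomes groups per pregnancy". Its outcome table assigns this test, with a relative risk and 95% confidence interval, to birth before 34 weeks and to most other outcomes.

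Section 7.2 powers the trial on the same test: "Group sample size of 121 in Group 1 and 121 in Group 2 achieve 80% power" and "The test statistic used is the two-sided Z test with pooled variance".

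The next sentence of 7.1 adds a multivariable logistic regression for confounding. It names no covariates and does not say whether this model or the Z test governs the conclusion.

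On prognosis, section 2.1 says: "This risk ranges from 11,1% with one previous preterm delivery up to 28% for two previous preterm deliveries". The same section gives 12% after a second-trimester loss beyond 20 weeks. Section 4.10.1 sets a minimum of one qualifying event and no maximum, so women with one event and women with several both enter.

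On allocation, section 10 says: "Every participating centre will have its own randomisation list". Centre is the only allocation factor stated; obstetric history is not mentioned.

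**The concern.** The protocol itself quantifies a strong baseline predictor: the ratio of the two risks is 0.28/0.111 = 2.52. The obstetric history has to be taken to check eligibility, so the count can be had before randomisation at almost no cost. The comparison on which the trial is sized does not use it, and the one analysis that might use it has no defined place.

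What is at stake is efficiency. An adjusted test removes the outcome variation due to history from the comparison, and it accounts for whatever imbalance in history arises by chance. It would also settle in advance which result governs if the crude and adjusted analyses disagree.

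**Working it through.** **Inputs from the documents.** Section 7.2: 121 women per arm. The treatment-arm proportion "is assumed to be 0,8 under the null hypothesis and 0,9240 under the alternative hypothesis". For control, "The proportion in Group 2 (the control group) is 0,8000". For alpha, "The significance level alpha of the test was 5" per cent, two-sided, pooled variance, 80% power. Section 2.1: risks of 11.1% and 28%.

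**Input not in the documents.** The share f of women with two or more previous events. Assumption: 10% to 50%, shown as a range.

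**Step 1: reproduce the plan's sample size.** The mean proportion is (0.924 + 0.80)/2 = 0.862.

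n = [1.96 × √(2 × 0.862 × 0.138) + 0.8416 × √(0.924 × 0.076 + 0.80 × 0.20)]² / 0.124² = (0.956 + 0.404)² / 0.01538 ≈ 120.3, rounded up to 121.

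Power at 121 per arm is 80.2%. The plan's figure is reproduced.

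**Step 2: variance explained by history.** With stratum risks 0.111 and 0.28, the overall risk is p = 0.111(1−f) + 0.28f and

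R² = f(1−f)(0.28 − 0.111)² / [p(1−p)].

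Adjustment acts roughly as if the sample were 121/(1−R²) per arm. Power is recalculated at that size for 0.80 versus 0.924.

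| f | p | R² | 121 × R² (women per arm) | Power |
|---|---|---|---|---|
| 10% | 12.8% | 2.3% | 2.8 | 81.2% |
| 20% | 14.5% | 3.7% | 4.5 | 81.7% |
| 30% | 16.2% | 4.4% | 5.4 | 82.0% |
| 40% | 17.9% | 4.7% | 5.7 | 82.1% |
| 50% | 19.6% | 4.5% | 5.5 | 82.0% |

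**Step 3: sensitivity to the event rate.** The overall risks above lie below the 20% control failure rate implied by section 7.2. Keeping the ratio of 2.52, and scaling the stratum risks so that the control arm averages 20% and the pessary arm 7.6%, gives a variance reduction of 3.1% to 4.6% and power of 81.5% to 82.1%. The conclusion does not change.

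**Step 4: simulation.** The pooled Z test was compared with a Cochran-Mantel-Haenszel test stratified by history (121 per arm, 40,000 runs per setting, f = 10%, 20%, 30% and 50%). Power was 81.4% to 81.7% crude and 81.9% to 82.6% stratified, a gain of 0.4 to 1.0 points within each setting. Type I error was 5.1% to 5.3% crude and 4.9% to 5.1% stratified. Centre was not simulated, because the protocol does not state the number of centres.

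**Step 5: size of a chance imbalance.** The standard deviation of the between-arm difference in f is √(2f(1−f)/121). At 1.96 standard deviations the difference is 7.6 points (f = 10%) to 12.6 points (f = 50%). Multiplied by 0.169, this moves the crude risk difference by 1.3 to 2.1 points. The standard error of that difference is √[(0.16 + 0.0702)/121] = 4.4 points, and the design difference is 12.4 points.

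**The case against.** The strongest reply is that nothing here is invalid. A pooled Z test suits a randomised two-arm comparison, matches the sizing and holds its level. Adjustment is planned in the very next sentence of 7.1, and its covariates may properly be left to an analysis plan that is not shown. On this view the proposal swaps one sound test for a slightly better one, for about one power point. All of that stands as to validity and size. It does not answer the point that the protocol itself fixes the less efficient test as the powered one.

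Three stronger readings are tempting, and the documents do not support them.

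- **Chance imbalance biases the result or inflates false positives.** Averaged over randomisation, the crude test's error rate is about 5%, and its standard error already covers such imbalance. One can obtain a higher rate by conditioning on an extreme imbalance in the pessary's favour, but the mirror-image imbalance lowers the rate correspondingly.
- **The share with two previous deliveries can be deduced as about 53%,** by treating the 20% control failure rate as a mix of 11.1% and 28%. Section 2.1 gives background risks of preterm birth. Section 7.2 does not name its endpoint, section 4.1.1 words the primary outcome as birth and survival of the child, controls receive progesterone (section 4.4), and women with only a late loss are eligible. The share is unknown.
- **The number of previous events is already a required data item.** Section 4.10.1 sets a yes-or-no threshold. The count comes from the same history, but it would have to be coded.

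It is also fair to say that section 2.1 gives a gradient by count only for preterm deliveries. The 12% after one late loss is close to the 11.1% after one preterm delivery, which supports putting a single event of either kind in the lower stratum. For two losses, or one of each kind, the higher risk is an assumption.

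**Conclusion.** The point holds as a modest gain in efficiency; it is not an error in the test. The crude comparison leaves unused about 2% to 5% of the outcome variance, equal to about 3 to 6 women per arm out of 121. Using it raises power from 80.2% to 81.2-82.1% by approximation, and by 1 point or less in simulation.

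This rests on two assumptions: that the gradient in section 2.1 carries over to the trial's endpoint in women treated under this protocol, and that 10% to 50% of women have two or more previous events. If the gradient is weaker, the gain shrinks towards zero.

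A reader might infer that the plan contains no adjustment, or that allocation must be stratified by history. Neither follows: a logistic model is planned, with its role left open, and a stratified analysis works with the centre lists as they stand.

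**What to change.** In sections 7.1 and 7.2, name the main comparison as a Cochran-Mantel-Haenszel test, reported with a Mantel-Haenszel relative risk and 95% confidence interval. Stratify by number of previous qualifying preterm deliveries or late losses (one versus two or more), as recorded before randomisation, and by centre, since centre is the factor used in randomisation. Keep the crude Z test as a supportive analysis. The sample size calculation can stay as it is, because it uses the less powerful test.

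The cost is a sentence in the statistics section and one coded history field on the case report form. No extra women are needed, and the promised relative risk and interval are retained. The one statistical drawback is slight information loss where a centre-by-history stratum is sparse, since a stratum with women in only one arm, or without events, adds nothing to the test. The randomisation lists need no change; adding history to them would double the strata of centre-specific lists in a trial of 242 women.
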